## 5. Number of Subjects

The primary outcome of this study is improvement in incontinence quality of life as measured by the ICIQ-SF Questionnaire. We used the previously reported means and standard deviation for this questionnaire (3) from a prior RCT on biofeedback and pelvic floor exercises. We have powered the study based on a 4-point difference as significant between groups. This 4-point difference used for the power calculation is based on prior studies and the minimally important difference that has been previously established (4). To achieve power for this non-inferiority RCT demonstrating a difference between groups of less than 4 points we need 21 patients per group (biofeedback versus PFPT) to detect no difference with an alpha =0.05 and

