## PROTOCOL TITLE: *SQEASI: Systematized Quality Exercise Alternatives for Stress Incontinence*

with 80% power. Allowing for a dropout of 20% we will enroll at least 50 patients (or 25/group), but up to 75 total.

This is a not a multi-center study. Data will be housed at the Eubank clinic

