## **13. Data Analysis**

Data Analysis: Between and within group differences will be evaluated using Fisher's exact test for categorical variables and t-tests for continuous variables. If there are any baseline differences between groups, a multivariate analysis will determine the contribution of these differences to observed differences (if any) between groups.

Power Analysis: Power analysis was performed based on previously reported means and standard deviation for the ICIQ-SF questionnaire. The primary outcome of this study is improvement in incontinence quality of life as measured by the ICIQ-SF Questionnaire. We used the previously reported means and standard deviation for this questionnaire (10) from a prior RCT on biofeedback and pelvic floor exercises. We have assumed a change score of greater than 4 points to be significant between groups based on prior studies and the minimally important difference that has been previously established (11). To achieve significance for a non-inferiority study using these assumptions we would need 42 patients, 21 per group to detect this difference with alpha =0.05 and with 80% power. To allow for a dropout of 20% we will enroll at least 50 patients, but up to 75 to account for participants who are lost to follow up.

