**III. Medical Devices**

The PeriCoach© biofeedback device will be used to measure pelvic floor muscle strength and provide guidance for patients to improve their pelvic floor exercises. These devices will be

PROTOCOL TITLE: *SQEASI: Systematized Quality Exercise Alternatives for Stress Incontinence*

provided for the 25 patients randomized to the biofeedback arm at the cost of the investigators. The devices are Bluetooth connected to the patient's smartphone and their profile collects password protected data based on the frequency and quality of their exercises on a secure smartphone application. We will request that the patient show researchers their profile at the 3 month visit to determine the frequency and quality of their exercise performance. The device has already been tested and validated for measuring pelvic floor muscle strength and treating female urinary incontinence and hence, its safety and effectiveness are not being evaluated in this study.

The FDA letter is attached.

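### Enrolment may end anywhere from 50 to 75 with no stated rule, and the floor of 50 falls short of the plan's own 42 completers

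*Combined protocol and SAP*

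**What the plan says.** Section 5 (Number of Subjects) sets the evaluable size from a 4-point margin: "demonstrating a difference between groups of less than 4 points we need 21 patients per group". Section 13 (Data Analysis) repeats it: "we would need 42 patients, 21 per group to detect this difference with alpha =0.05 and with 80% power". Neither section says whether alpha is one-sided or two-sided. The SD is not printed; Section 5 only points to a source: "We used the previously reported means and standard deviation for this questionnaire (3) from a prior RCT on biofeedback and pelvic floor exercises".

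For enrolment, Section 5 says "Allowing for a dropout of 20% we will enroll at least 50 patients (or 25/group), but up to 75 total". Section 13 adds a reason for the upper figure: "we will enroll at least 50 patients, but up to 75 to account for participants who are lost to follow up". Sections 6 and 12 repeat the maximum of 75. The device checklist (Checklist III, Medical Devices) describes devices "provided for the 25 patients randomized to the biofeedback arm".

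Four other statements bear on the point:
- Section 3 describes the trial as unmasked.
- Section 12 has research staff and clinicians administer the questionnaires.
- Section 14 says there is no DSMB.
- Section 6 estimates 10-20 eligible women a month with half enrolling, follows each woman for 3 months, and places analysis after those data are collected.

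**The concern.** A minimum and a maximum that differ by 25 women leave the final number to someone's discretion. The documents do not say who decides, on what information, or when. In an unmasked trial, 3-month scores from the earlier women exist while later women are still being enrolled. Nothing says those scores stay unsummarised by arm until enrolment closes. If the decision to stop followed the between-arm result, the final test would no longer have exactly its stated error rate.

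The ends of the range also do not match the rest of the plan. The minimum is presented as allowing for 20% dropout, but it does not leave the required completers after a 20% loss. The maximum needs more devices than the checklist provides for.

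**Working it through.** **Inputs from the documents.** Margin 4 points, 21 per group (42 total), alpha 0.05, power 80%, dropout 20%, enrolment 50 to 75 (Sections 5 and 13); 10-20 eligible women a month, 50% enrolling, 3-month follow-up (Section 6); 25 devices (Checklist III). **Assumptions.** 1:1 allocation, inferred from the equal group sizes; true difference 0 for power and 4 points for type I error; SD back-solved.

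**1. The plan's own 21 per group.** With n = 2·SD²·(z₁₋α + z₀.₈)²/4², rounded up, n = 21 results for an SD of 5.09-5.21 at one-sided 0.05, or 4.52-4.62 at one-sided 0.025. With no SD printed, 21 can be shown to be possible but not confirmed. Solving with a t-test instead of the normal approximation, 80% power at 21 per group corresponds to SDs of about 5.12 and 4.51.

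**2. Dropout inflation.**
- Per group: 21/(1 − 0.20) = 26.25, so 27, or 54 in total. Check: 27 × 0.80 = 21.6, whereas 26 × 0.80 = 20.8.
- 50 enrolled: 50 × 0.80 = 40 completers, 2 short. Fifty covers a loss of 1 − 42/50 = 16%. Multiplying instead of dividing gives 42 × 1.20 = 50.4, which may be where 50 came from.
- 75 enrolled: 75 × 0.80 = 60 completers. Ending with 42 would take a loss of 1 − 42/75 = 44%.

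**3. Power at the ends of the range.** Power = Φ(4/(SD·√(2/n)) − z₁₋α).
- n = 20 per group, SD 5.21, one-sided 0.05: 4/(5.21 × 0.3162) − 1.645 = 0.783, so Φ = 78%.
- n = 20 per group, SD 4.62, one-sided 0.025: 4/(4.62 × 0.3162) − 1.960 = 0.778, so Φ = 78%.
- t-test with SDs 5.12 and 4.51: also about 78%. At the lower end of the normal-approximation SD ranges, power at 20 per group is just under 80%.
- n = 30 per group (75 enrolled, 20% lost), SDs 5.21 and 4.62: about 91% and 92%.

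**4. Does the calendar fix the number?** Enrolment of 5-10 a month for 12 months gives 60-120 women. It does not.

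**5. Outcome lag.** At 5-10 enrolments a month and 3 months to outcome, 15-30 enrolled women have no 3-month score at any given moment.

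**6. Type I error at the margin.** These are simulated trials with a true difference of 4 and no dropout. Enrolment stops when an unadjusted test on the outcomes then available succeeds, with a look at every enrolment from 50 to 75. The final test uses all women enrolled. The SDs were 5.12 and 4.51. At the margin the t statistic is scale-free, so this choice does not drive the result.

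| Scenario | Nominal 5% | Nominal 2.5% |
|---|---|---|
| Number fixed in advance, or driven only by losses | 5.0% | 2.5% |
| Continuous looks, 15-30 women without outcomes | 5.6-6.4% | 2.9-3.3% |
| Continuous looks, outcomes known at once (no lag) | 10.7% | 5.9% |

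The shorter lag gives the higher figures in the second row. The third row does not describe this trial, because the primary outcome arrives at 3 months.

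**7. Devices.** 75/2 = 37.5, so about 37-38 biofeedback women at the maximum, against 25 provided for.

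**The case against.** A range for the sample size does not by itself raise type I error; unadjusted between-arm looks that decide when to stop would. The documents plan no such look, and Section 6 puts analysis after follow-up. Section 13 gives retention, not outcome, as the reason for going above 50. Being unmasked makes a look possible but is not evidence of one, and no section says who ends enrolment. All of this stands.

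A reader might infer that the trial does not hold its alpha, or that the error doubles to about 10.7%. The documents do not support that. The doubled figure requires outcomes to be known at enrolment, or enrolment to pause until they are known. Neither is described.

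A reader might also infer that dropout has been counted twice, once to reach 50 and again to reach 75. Section 13 can equally be read as a floor sized for 20% loss with headroom if loss is worse. The 44% figure is what headroom up to 75 would cover, not proof of double counting.

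The device mismatch has no bearing on alpha and arises only if enrolment exceeds 50. What the objection does not answer is that headroom for losses still needs a rule saying how many losses lead to how many further women, and that 50 does not deliver 42 at the plan's own 20%.

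**Conclusion.** The point holds as a gap in the text, not as a demonstrated failure of error control. Enrolment between 50 and 75 has no target, no trigger and no statement that between-arm data stay unseen until it closes. If that discretion were used on outcomes, the excess would be about 0.6-1.4 percentage points at nominal 5% (5.6-6.4%), or 0.4-0.8 at nominal 2.5% (2.9-3.3%). This assumes the enrolment rate and follow-up time in Section 6 and no dropout.

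The shortfall at the floor is arithmetic from the plan's own figures: 40 completers instead of 42. The resulting power of about 78% rests on a back-solved SD, because the plan prints none. The device count agrees with the floor only. Each item is small, but they can be closed together in a few sentences.

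**What to change.** In Sections 5 and 13, replace the open range with one of two rules:
- a single target of 54 enrolled, 27 per group; or
- a trigger based only on completer counts: enrol until 42 women have completed, 21 per group, with a cap of 75.

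Under the second rule, state that women already enrolled when the trigger is met finish follow-up and are analysed. Because of the lag it may overshoot: about 53 enrolled to yield 42 completers (42/0.80 = 52.5), plus 15-30 still in follow-up, is 68-83, so the cap may be what ends enrolment. The fixed target avoids this.

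Under either rule, repeat the same number in Sections 6 and 12, state that no ICIQ-SF data are summarised by arm before enrolment closes, and reconcile the device count in Checklist III with the number chosen.

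The cost is wording in these sections and less flexibility on the final number, plus at least two devices beyond the 25 described (27 − 25). No visit or assessment changes.

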### 6. Study Timelines

Based on current clinic volume in the UNM division of Urogynecology, we estimate recruitment of up to 75 patients would be feasible over a 12 month period. A review of our clinic calendar revealed in 1 months' time, the urogynecology division typically sees 10-20 patients who would meet criteria for our study. Assuming 50% enrollment, we will be able to recruit our projected number of patients in 12 months. Additionally, as subjects will be followed for 3 months after randomization, we expect it may take up to 15 months to collect 3 month follow up data. We estimate that data analysis and composition of the manuscript will take an additional 10 months.

Timeline	July 2018- Oct 2019	Nov 2019-Feb 2020	Mar 2017-May 2020
Subject recruitment, therapy, through 3 month follow up	←→		
Data analysis		←→	
Manuscript preparation		←→	

### 7. Study Endpoints

The **primary endpoint** of our study is to determine the 3 month change in ICIQ-SF score between the women who undergo PFPT compared to those who undergo home biofeedback therapy for stress urinary incontinence. Our secondary endpoints include patient report of symptomatic cure or improvement and cost effectiveness between techniques and cost of intervention. Our **exploratory endpoints** are to investigate compliance with treatment between groups, preference if given choice between options, and differences in sexual function 3 months after initiation of therapy between the two groups. Desire for further treatment will also be assessed.

Given the extremely low-risk nature of the therapeutic interventions, we do not have any **safety endpoints**.

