## 1. Objectives

The objective of this research is to perform a non-blinded, non-inferiority randomized controlled trial to assess the quality of life (QOL) of women with stress urinary incontinence (leakage of urine with cough or sneeze) before and after conservative treatment with either pelvic floor physical therapy (PFPT) or home biofeedback. The target population are patients with stress urinary incontinence (SUI) who are seeking care and desire non-surgical management. Our central hypothesis is that home biofeedback will be non-inferior to pelvic floor physical therapy and both will equally improve quality of life for women with stress urinary incontinence. The specific aims are:

**Aim 1:** To compare quality of life, as measured by the International Consultation Incontinence Questionnaire-Short Form (ICIQ- SF), in women with stress predominant incontinence before and after PFPT versus home biofeedback application after 3 months of therapy. Secondary outcomes related to this aim include improvements in urinary incontinence severity as measured by the Incontinence Severity Index (ISI) and desire to pursue additional therapy (such as pessary or surgery) at the conclusion of the study.

**Hypothesis:** Home biofeedback will demonstrate equal improvement in QOL in women with SUI compared to PFPT.

**Aim 2:** To perform a comparative analysis of cost between PFPT treatment and home biofeedback for stress predominant incontinence as well as patient preference for either PFPT vs home biofeedback. **Hypothesis:** Home biofeedback will be less expensive than PFPT due to decreased copays, driving to visits, with similar success rates and women will prefer to have home therapy.

**Aim 3:** To determine whether patients experience improvement in sexual function following treatment using the Pelvic Organ Prolapse Incontinence Sexual Questionnaire- 12 and Female Sexual Function Index (FSFI). **Hypothesis:** Both groups will report improved sexual function.

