Three months after starting active treatment, all participants will have a return visit to discuss progress, which is consistent with our standard care for these patients. If the participant had a delay in starting PFPT, the follow up visit will occur 3 months after first PT appointment. At the 3 month visit the patient will complete the ISI, ICIQ-SF, EQ-5D, OAB-q SF, PISQ-12, FSFI, and PGI-I. We will also ask the patient which treatment she would prefer if given the option, the level of satisfaction she has with the current treatment, and if she is planning any future surgical procedures or treatment for her stress incontinence. A physical exam will assess pelvic floor strength using the Modified Oxford Grading Scale and a cough stress test will be performed. If the patient is unable to return to clinic, a member of the research team will call the patient to administer the surveys over the phone. If unable to contact the patient 3 times, we will discontinue attempts and the patient will be considered lost to follow up.

Table 1: Outcomes collected at various time points

	Baseline	3 months
Demographic and medical history	X	
ISI	X	X
Revised Oxford Scale	X	X
ICIQ-SF	X	X
EQ-5D	X	X

FSFI	X	X
OAB-q SF	X	X
PISQ-12	X	X
PGI-I		X
Follow up Questionnaire		X

Our primary outcome is changes in QOL at 3 months after treatment initiation as measured by the ICIQ-SF. It is our standard of care to see patients back at 3 months following SUI treatment initiation to assess for continued leakage and offer further conservative or surgical management. Therefore, as part of a secondary aim we will assess sexual function, compliance with treatment between groups, preference between 2 options, and desire for further treatment at this 3 month time point.

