#### Outcome Measures:

1. **Pelvic Organ Prolapse Quantification (POP-Q):** This is a validated scale adopted by IUGA/ICS and described in their 2010 joint report. It aims to measure the degree of POP where the hymen is the fixed point of reference for description. (5)
2. **Modified Oxford grading system:** This applies a 6-point scale to rate the muscle strength of the pelvic floor where, strength is as follows:  
0 = no contraction; 1 = flicker; 2 = weak; 3 = moderate; 4 = good; 5 = strong (6)
3. **The Pelvic Organ Prolapse/Incontinence Sexual Questionnaire, 12 (PISQ-12):** This is a brief validated, reliable and responsive measure of women's sexual function in those with pelvic floor disorders. (7)
4. **Incontinence Severity Index (ISI):** This is a validated questionnaire that has been shown to correlate well with pad weighing tests. (8)
5. **Patient's Global Impressions of Improvement (PGI-I):** This is a validated 1-item questionnaire rating specific condition as perceived change in her condition in response to therapy for SUI. (9)
6. **The International Consultation Incontinence Questionnaire-Short Form (ICIQ- SF)** This validated scale is a condition-specific assessing QOL of women with urinary incontinence. The most recent Cochrane review on Biofeedback recommends using this scale in trials using biofeedback for urinary incontinence. (10,11)
7. **Female Sexual Function Index (FSFI):** A brief questionnaire measure of sexual functioning in women that assesses arousal, orgasm, satisfaction and pain. (12)
8. **European Quality of Life-5 Dimensions (EQ-5D):** Preference-based utility index algorithm used to calculate each subject's utility index and compare change in QALYs between treatment groups (13).
9. **Overactive Bladder Questionnaire- short form (OAB-q SF):** Symptom bother scale that captures the full spectrum of OAB symptoms and health related quality of life (14).

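### The secondary outcome lists in Sections 1, 7 and 12 conflict, and Aim 2's hypothesis of similar success rates has only a test for a difference behind it

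*Combined protocol and SAP*

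**What the plan says.** All references are to the combined protocol and SAP.

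- **Section 1, Aim 1:** "Secondary outcomes related to this aim include improvements in urinary incontinence severity as measured by the Incontinence Severity Index (ISI"), together with the wish to pursue further therapy at the end of the study.
- **Section 1, Aim 2 hypothesis:** home biofeedback will cost less "with similar success rates and women will prefer to have home therapy". Success is not defined.
- **Section 7:** "Our secondary endpoints include patient report of symptomatic cure or improvement and cost effectiveness between techniques and cost of intervention". The ISI does not appear. Compliance, preference and sexual function are listed as exploratory, and desire for further treatment is mentioned after them without a tier.
- **Section 12, end of the procedures text:** sexual function, compliance, preference and desire for further treatment are assessed under a secondary aim. Neither the ISI nor cure or improvement is in that list.
- **Section 12, 3-month visit:** "At the 3 month visit the patient will complete the ISI, ICIQ-SF, EQ-5D, OAB-q SF, PISQ-12, FSFI, and PGI-I". Also, "A physical exam will assess pelvic floor strength using the Modified Oxford Grading Scale and a cough stress test will be performed".
- **Section 12, Outcome Measures, on the PGI-I:** "This is a validated 1-item questionnaire rating specific condition as perceived change in her condition in response to therapy for SUI". No response level is called cure, improvement or success.
- **Section 13:** "Between and within group differences will be evaluated using Fisher's exact test for categorical variables and t-tests for continuous variables". The 4-point value in Sections 5 and 13 applies to the ICIQ-SF only.

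**The concern.** There are two linked faults.

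First, the reader cannot tell which outcomes are secondary. Aim 1 and Section 7 name different efficacy outcomes. Section 12 gives a third list, which moves three outcomes from the exploratory tier to a secondary one. Cure, improvement and success are not tied to an instrument or a response level, although the ISI, the PGI-I, the ICIQ-SF and a cough stress test are all collected at 3 months. In an unmasked trial these choices should be fixed before the data are seen.

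Second, Aim 2 states a hypothesis of similarity, while the plan's only tool for a rate is a test of difference. Failing to find a difference in a trial of this size says little about whether the rates are close. What is at stake is a secondary claim, that the cheaper option works about as often, which the planned analysis cannot establish.

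**Working it through.** **Comparing the lists**

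| Outcome | Section 1 | Section 7 | Section 12 |
|---|---|---|---|
| ISI improvement | secondary (Aim 1) | not listed | collected, not in the secondary-aim list |
| Patient-reported cure or improvement | not listed | secondary | not in the secondary-aim list |
| Desire for further therapy | secondary (Aim 1) | mentioned after the exploratory endpoints | secondary aim |
| Sexual function | Aim 3 | exploratory | secondary aim |
| Preference | Aim 2 | exploratory | secondary aim |
| Compliance | not listed | exploratory | secondary aim |

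No outcome in the table has the same status in all three sections.

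**The plan's own figure.** The only sample size stated is 21 per group for the ICIQ-SF (4-point difference, alpha 0.05, 80% power). It cannot be reproduced directly because the SD is not printed. It would follow from an SD of about 5.1 to 5.2 (non-inferiority, one-sided 0.05) or 4.5 to 4.6 (one-sided 0.025). No figure is given for any rate, so there is none to reproduce for this point.

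**Inputs for the rates**

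- Arm sizes: 21 per arm is the stated requirement. With 75 enrolled and 20% lost, 75 × 0.8 = 60, or 30 per arm. With 75 enrolled and none lost, about 37 per arm.
- True success rates: not in the documents. Assumed 60 to 80% with PFPT, with home biofeedback 20 or 30 points lower.
- Test: two-sided Fisher's exact test at 0.05, taking alpha 0.05 as two-sided.

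**Probability of a non-significant result.** For n per arm and true rates p1 and p2, sum Bin(i; n, p1) × Bin(j; n, p2) over all pairs (i, j) whose Fisher p-value exceeds 0.05. This was done by full enumeration.

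| True rates | 21 per arm | 30 per arm | 37 per arm |
|---|---|---|---|
| 70% vs 50% | 84% | 74% | 68% |
| 70% vs 40% | 64% | 44% | 34% |
| 20-point deficit, PFPT rate 60 to 80% | 81–85% | 70–74% | 62–69% |
| 30-point deficit, PFPT rate 60 to 80% | 60–64% | 40–44% | 29–34% |

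**A single example.** At 21 per arm, 15/21 against 8/21 is an observed gap of 7/21 = 33 points, and Fisher's test gives p = 0.06.

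**Precision.** The 95% half-width for the difference is 1.96 × √(2p(1−p)/n). At p = 0.6 and n = 21 this is 1.96 × √(0.48/21) = 0.296, or about 30 points. At p = 0.8 and n = 21 it is about 24 points. At p = 0.6 and n = 37 it is about 22 points.

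**The case against.** The strongest reply is that this is a matter of drafting. Both Aim 1 and Section 7 introduce their lists with a word that leaves them open, so the ISI's absence from Section 7 may be incomplete listing, not replacement, and the ISI is collected at both visits. The PGI-I is the natural source for patient-reported improvement. The phrase on success rates sits inside a cost hypothesis, and the cost analysis itself runs on EQ-5D QALYs. The primary outcome is consistently the 3-month ICIQ-SF.

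Much of this stands. It limits the importance of the point but does not remove it: the tiers still contradict each other for sexual function, compliance and preference, the link to the PGI-I is never made, and a comparative statement about success remains without a definition or a suitable analysis.

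Three stronger readings are tempting and are not supported.

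- A reader might infer that the investigators will declare similarity from a non-significant test. Section 13 says only that differences will be evaluated. The plan leaves that reading open because it gives no other criterion, but it does not state it.
- A reader might infer that a principal secondary endpoint has been defined in three incompatible ways. The plan ranks no secondary endpoint above the others, and the success rate in Aim 2 is not a listed endpoint.
- A reader might infer that an open success definition badly inflates false positives. Fisher's test is conservative here: with an assumed latent correlation of 0.5 and true rates of 60 to 70%, any significant result at 21 per arm occurs about 6% of the time across three definitions and 7–8% across four. That is also the error of falsely finding a difference, not of falsely accepting similarity.

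**Conclusion.** The point holds as a fault in secondary outcomes. The current lists in Sections 1, 7 and 12 contradict each other, and the stated analysis cannot support the stated hypothesis of similar success. Under the assumed rates, a 30-point deficit for home biofeedback would go undetected about 60–64% of the time at 21 per arm and still about 29–34% of the time at 37 per arm, so enrolling the maximum does not cure it. These probabilities rest on assumed success rates and a two-sided 5% test. The conflict between the lists and the absence of a margin or interval rest on the text alone. The primary ICIQ-SF comparison is not touched by this point.

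**What to change.** 1. **Sections 1, 7 and 12:** carry one identical secondary list. Keep ISI change at 3 months and desire for additional therapy, and add patient-reported improvement and cure as separate items beside the cost outcomes. Give sexual function, compliance and preference the same tier wherever they appear.
2. **Definitions:** tie improvement to the PGI-I and report cure separately from the ISI. Take the response levels from the instruments, because the documents do not print them, and fix them before any outcome data are examined. Use the PGI-I improvement rate as the success rate in Aim 2.
3. **Section 13:** report each rate as a between-arm difference with a 95% confidence interval, and state that a non-significant Fisher test will not be read as similarity.
4. **Aim 2 hypothesis:** replace the similarity phrase with a statement that the difference in success rate will be reported with its 95% confidence interval.

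The cost is wording in four sections. No new instrument, visit or participant is needed. The plan gives up a claim of similar success that a sample of this size could not support.
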